##### Measurement Technique

The chart should be at a comfortable viewing angle. The right eye should be tested first. The subject should attempt to read each letter, line-by-line, left to right, beginning with line 1 at the top of the chart. The subject should be told that the chart has letters only, no numbers. If the subject reads a number, he or she should be reminded that the chart contains no numbers, and the examiner should then request a letter in lieu of the number. The subject should be asked to read slowly, so as to achieve the best identification of each letter. He/she is not to proceed to the next letter until he/she has given a definite response.

If the subject changes a response (e.g., 'that was a "C" not an "O"') before he has read aloud the next letter, then the change must be accepted. If the subject changes a response having read the next letter, then the change is not to be accepted. The examiner should never point to the chart or to specific letters on the chart during the test.

A maximum effort should be made to identify each letter on the chart. When the subject says he or she cannot read a letter, he or she should be encouraged to guess. If the subject identifies a letter as one of two letters, he or she should be asked to choose one letter and, if necessary, to guess. When it becomes evident that no further meaningful readings can be made, despite encouragement to read or guess, the examiner should stop the test for that eye. However, all letters on the last line

should be attempted as letter difficulties vary and the last may be the only one read correctly. The number of letters missed or read incorrectly should be noted.

LogMAR Visual Acuity Calculations

The last line in which a letter is read correctly will be taken as the base logMAR reading. To this value will be added the number " $N \times 0.02$ " where 'N' represents the total number of letters missed up to and included in the last line read. This total sum represents the logMAR visual acuity for that eye.

For example: Subject correctly reads 4 of 5 letters on the 0.2 line, and 2 of 5 letters on the 0.1 line.

|  |               |
|--|---------------|
| Base logMAR  | = 0.1         |
| N (total number of letters incorrect on line 0.2 as well as 0.1) | = 4           |
| $N \times T$ (T=0.02)  | = 0.08        |
| Base logMAR + (N × T)  | = 0.1 + 0.08  |
| logMAR VA   | = 0.18 |

Repeat the procedure for the left eye.

In order to provide standardized and well-controlled assessments of visual acuity during the study, all visual acuity assessments at a single site must be consistently done using the same lighting conditions and same correction if possible during the entire study. If the same correction cannot be used (ie, a subject forgets his glasses), the reason for the change in correction should be documented.

Gonioscopy (Both eyes)

Gonioscopy will be graded with the Shaffer scale:

| Shaffer Scale  |                                     |                      |
|----------------|-------------------------------------|----------------------|
| Classification | Finding                             | Angle width (degree) |
| Grade 4        | Ciliary body is visible             | 35-45                |
| Grade 3        | Scleral spur is visible             | 20-35                |
| Grade 2        | Only trabecular meshwork is visible | 20                   |
| Grade 1        | Only Schwalbe's line is visible     | ≤10                  |
| Grade 0        | Angle is closed                     | 0                    |

### **Automated Perimetry**

(Each Eye, if applicable: required only if there is no data within the past 6 months)

Automated perimetry will be performed as indicated in the study flowchart in [Appendix 1](#). If the brow is heavy or the upper lid is drooping, tape accordingly. Visual field results must be reliable (i.e.,  $\leq 33\%$  fixation losses, false positive or false negative errors) or the field should be repeated within two weeks. Visual field examinations will be performed using an automated perimetry test preferably Humphrey automated perimeter (full threshold 24-2 program or SITA standard). Preferred equipment is the Humphrey 700 HFA-2 series machines (eg, 740 or 750). Visual fields will be reported as normal or abnormal and the mean deviation will also be recorded in decibels.

Begin by testing the right eye. Adjust the chin rest and the table height as needed to achieve proper alignment as well as to maintain the subject in a comfortable seated position throughout the test. It is permissible to encourage the subject occasionally if the subject seems to be fatigued or losing concentration, and to allow the subject to pause and rest if necessary. The subject should also be informed that a good time to blink is when the response button is pushed so as not to affect the results of the test.

### **Slit Lamp Biomicroscopy (Each Eye)**

Biomicroscopy will be performed using a slit lamp. Magnification will be consistent with standard clinical practice at every visit. The subject will be seated.

This will be done to observe the overall health of the eye, including the lid/lashes, conjunctiva, cornea anterior chamber, iris, and lens. Any observations at the screening visit will be recorded as ocular medical history, and any new or worsened observations may be recorded as AEs. Observations will be graded as Normal or Abnormal. Abnormal findings which are clinically significant will be described.

### **Goldmann Applanation Tonometry (Each Eye)**

The time of tonometry will be recorded on the source document for all visits. Measurements will be taken by two qualified independent study site personnel using a Goldmann applanation tonometer affixed to a slit lamp with the subject seated. One person will adjust the dial in masked fashion and a second person will read and record the value. The subject and slit lamp should be adjusted so that the subject's head is firmly positioned on the chin rest and against the forehead rest without leaning forward or straining. Both eyes will be tested, with the right eye preceding the left eye. Each IOP measurement is to be recorded.

One person ("the measurer") looks through the binocular viewer of the slit lamp at low power. The tension knob is pre-set at a low pressure value (4 to 6 mmHg). The measurer follows the image of the fluorescein-stained semicircles while he/she slowly rotates the tension knob until the inner borders of the fluorescein rings touch each other at the midpoint of their pulsation in response to

the cardiac cycle. When this image is reached, the measurer takes his/her fingers off the tension knob and the second person (“the reader”) records the IOP reading along with the date and time of day in the source document, thus maintaining a masked IOP reading.

At least two, and if necessary, three consecutive measurements will be taken to determine IOP in the manner described above. After first measurement remove applanator (prism) from the corneal surface, reset the dial to low number, reapply applanator and re-measure.

If the first two measurements differ by 1 mmHg or less, a third measurement is not required, the two measurements will be recorded and the mean IOP of the two measurements will be recorded and used in the analysis. If the first 2 measurements differ by more than 1 mmHg, a third measurement should be made, all 3 measurements will be recorded and the median IOP of the three measurements will be recorded and used in the analysis.

### **Corneal Pachymetry**

*(Each Eye, if applicable: required only if there is no data in the subject’s file within past 30 days)*

Central corneal thickness measurements of each eye will be performed using an ultrasonic pachymeter and as indicated in the study flowchart in [Appendix 1](#). Measurements will be made before IOP is taken. For ultrasound probes, the Probe Quality Factor must be greater than or equal to 85%. With the subject seated and visualizing a consistent fixation target, position the probe tip on the cornea, perpendicular to the corneal surface, on the visual axis (ie, centered on the pupil). Once the probe tip is positioned properly, take a measurement. A total of 3 acceptable measurements, as described above, should be made for each eye, and the 3 measurements will be recorded in microns.

### **Dilated Ophthalmoscopy (Each Eye)**

Dilated exam will be performed after tonometry. The examination will not be performed until the subject’s eyes are deemed sufficiently dilated in the opinion of the investigator. The investigator will note any findings present and whether or not the findings are clinically significant or not clinically significant. Findings which are clinically significant will be described. The following will be examined:

- Vitreous
- Retina
- Macula
- Choroid
- Optic Nerve
- Cup-to-Disc Ratio (may be assessed using slit lamp following dilation)

**Additional Study Supplies:**

- Urine pregnancy test
- Study medication dosing diary
- Fluorescein and anesthetic for IOP measurement
- Dilating drop(s) for ophthalmoscopy exam
- Anesthetic for gonioscopy
- Lubricating gel for gonioscopy (if applicable)

## Appendix 2 Contraceptive Guidance

### Definitions:

#### *Woman of Childbearing Potential (WOCBP)*

A woman is considered fertile following menarche and until becoming postmenopausal unless permanently sterile (see below).

#### *Women in the following categories are not considered WOCBP*

1. Premenarchal
2. Premenopausal female with 1 of the following:
  - a) Documented hysterectomy.
  - b) Documented bilateral salpingectomy.
  - c) Documented bilateral oophorectomy.Note: Documentation can come from the study center personnel's: review of the subject's medical records, medical examination, or medical history interview.
3. Postmenopausal female:
  - a) A postmenopausal state is defined as no menses for 12 months without an alternative medical cause. A high follicle stimulating hormone (FSH) level in the postmenopausal range may be used to confirm a postmenopausal state in women not using hormonal contraception or hormonal replacement therapy (HRT). However, in the absence of 12 months of amenorrhea, a single FSH measurement is insufficient.
  - b) Females on HRT and whose menopausal status is in doubt will be required to use 1 of the non-estrogen hormonal highly effective contraception methods if they wish to continue their HRT during the study. Otherwise, they must discontinue HRT to allow confirmation of postmenopausal status before study enrollment.

### Contraception Guidance

#### *Male subjects*

- Male subjects with female partners of childbearing potential are eligible to participate if they agree to ONE of the following during the Clinical Investigational Plan-defined time frame in Section 5.3
  - Are abstinent from penile-vaginal intercourse as their usual and preferred lifestyle (abstinent on a long-term and persistent basis) and agree to remain abstinent.
  - Agree to use a male condom plus partner use of a contraceptive method with a failure rate of <1% per year as described below when having penile-vaginal intercourse with a woman of childbearing potential who is not currently pregnant.

- Male subjects with a pregnant or breastfeeding partner must agree to remain abstinent from penile-vaginal intercourse or use a male condom during each episode of penile penetration during study period (until Visit 5).

### ***Female subjects***

Female subjects of childbearing potential are eligible to participate if they agree to use a highly effective method of contraception consistently and correctly as described in the table below.

### **Highly Effective Contraceptive Methods**

|  |
|--|
| 
Highly Effective Contraceptive Methods That Are User Dependenta
Failure rate of <1% per year when used consistently and correctly.
  |
| 
Combined (estrogen and progestogen containing) hormonal contraception associated with inhibition of ovulation
Oral.
Intravaginal.
Transdermal.
  |
| 
Progestogen only hormonal contraception associated with inhibition of ovulation
Oral.
Injectable.
   |
| 
Highly Effective Methods That Are User Independenta
   |
| 
Implantable progestogen only hormonal contraception associated with inhibition of ovulation
Intrauterine device (IUD).
Intrauterine hormone-releasing system (IUS).
Bilateral tubal occlusion.
  |
| 
Vasectomized partner
A vasectomized partner is a highly effective birth control method provided that the partner is the sole male sexual partner of the WOCBP and the absence of sperm has been confirmed. If not, an additional highly effective method of contraception should be used.
   |
| 
Sexual abstinence
Sexual abstinence is considered a highly effective method only if defined as refraining from heterosexual intercourse during the entire period of risk associated with the study treatment. The reliability of sexual abstinence needs to be evaluated in relation to the duration of the study and the preferred and usual lifestyle of the subject.
 |
| 
NOTES:
aTypical use failure rates may differ from those when used consistently and correctly. Use should be consistent with local regulations regarding the use of contraceptive methods for subjects participating in clinical studies.
   |

### **Pregnancy Testing:**

- WOCBP should only be included after a confirmed menstrual period and a negative highly sensitive urine pregnancy test at screening and at Visit 2 and Visit 4.

6.1.1 Primary Objectives

To evaluate the therapeutic equivalence of TID dosing (will be done approximately 8.00 AM. (±60 minutes), 4.00 PM. (±60 minutes) and 10.00 PM. (±60 minutes) of SPIL's Brinzolamide ophthalmic suspension USP 1% (10mL) w/v compared with Azopt® 1% (10mL) in subjects with open-angle glaucoma or ocular hypertension.

6.1.2 Secondary Objectives

The secondary objective is to evaluate the safety of TID dosing of SPIL's Brinzolamide ophthalmic suspension USP 1% w/v compared with Azopt® 1% in subjects with open-angle glaucoma or ocular hypertension.

7 Study Design

7.1 Overview

7.1.1 Study Design

[figure not shown]
This is a randomized, Investigator-masked, multiple-center, parallel-group, therapeutic equivalence study with clinical endpoint (endpoint is mean difference in IOP of both eyes between the 2 treatment groups).

Treatment period will consist of TID dosing for 6 weeks. Subjects who are chronically treated with ocular hypotensive medications are required to undergo appropriate washout periods prior to study entry to minimize any residual effects of other active ocular hypotensive medications.

Page 9 of 21

. This is a controlled version of the document, unauthorized use, print or

Page 10 of 21

7.1.2 Treatment Groups

Approximately 666 subjects (333 per treatment arm) will be randomized in this study in a 1:1 treatment allocation ratio. The study will be conducted in Russia and India, out of 666 subjects466 subjects will be recruited in Russia and 200 subjects will be recruited in India.

IMP: Brinzolamide ophthalmic suspension USP 1% w/v, 10mL.

RLD: Azopt® 1% (brinzolamide ophthalmic suspension), 10mL.

7.2 Study Endpoints

7.2.1 Primary Efficacy Endpoint

Primary endpoint of this study is to assess the mean difference in IOP of both eyes between the two treatment groups dosed in each eye TID approximately at 8.00 AM. (±60 minutes), 4.00 PM. (±60 minutes) and 10.00 PM. (±60 minutes) and sample collected at four time points, i.e., at approximately 8:00 a.m. (hour 0; before the morning drop) and 10:00 a m. (2 hours) at the Day 14 (Week 2) and Day 42 (Week 6) visits.

7.2.2 Secondary Efficacy End point

Change from baseline in IOP of both eyes between the 2 treatment groups at 4 time points, i.e., at approximately 8:00 a m. (hour 0; before the morning drop) and 10:00 a.m. (hour 2) at the Day 14 (Week 2) and Day 42 (Week 6) visits.

7.2.3 Safety Assessments

- Incidence and severity of AEs
- BSCVA
- Slit lamp Biomicroscopy
- Tonometry
- Dilated fundus exam, including Cup/Disc ratio

Statistical Analysis P Sponsor: Sun Pharm	tries Ltd	
		Date: 20 Sep 2023

8 General Statistical Considerations

8.1 Descriptive Statistics

The following descriptive statistics will be calculated for continuous data and for categorical data:

Summary statistics are displayed with the following digits:

Description	Characteristic	Number of
Description	Characteristic	decimal places
Count	n	0
Count corresponding to the number of patients for a group	N	0
Mean	Mean	As in source + 1
Standard Deviation	SD	Mean+1
Minimum	Min	As in source
Median	Median	As in source + 1
Maximum	Max	As in source
Percentage relative to N #	%	1
Confidence Interval	CI	Respective Estimate+2
1st Quartile / 3rd Quartile	Q1/Q3	As in source + 1

[#] Number of decimal places can be more than one, if necessary. All table percentages should be rounded to one decimal place if not stated otherwise.

All data will be presented in the subject data listings.

If either table or listing does not include any observation, then the following placeholder will be used: "NO DATA CONTRIBUTED TO THIS TABLE / LISTING".

8.2 Analysis Population

Analysis Population	Definition
All Screened Population	All patients who have signed the informed consent form
Intent-to-Treat Population	The Intent-to-Treat (ITT) population consists of all subjects who are randomized into the study. and ITT based analysis will be used as confirmatory analyses
Per Protocol Population	The PP population includes all randomized subjects who meet all inclusion/exclusion criteria, and complete evaluations at week 2, week 6 (with compliance between 75 to 125%) with no major protocol deviations that would affect the treatment evaluation (primary endpoint). The PP population will be considered the primary analysis population for the study and will summarize subjects as treated.
Safety Population	The safety population includes all subjects who receive at least 1 dose of study medication. The safety population will be used to summarize safety variables and will summarize subjects as treated.

Note: As there are multiple examples of violations to GCP and ALCOA principles, all the data reported from Site # 122 is not reliable. Hence, based on the clinical investigation report dated 13 Sep 2023, it has been agreed to remove all the 20-subject data from the efficacy analysis These 20 subjects will be included in the safety analysis of the study data. However, safety data will be presented with and without subjects from Site #122.

8.3 Definitions

In the following table, the definitions and calculation of derived variables are summarized.

Variable / Term	Definition / Way of calculation
Treatment Start Date	Date of dose administration on Day
Treatment End Date	Date of Last Study Medication Taken in EoS page in CRF
Duration of exposure	Treatment end date- treatment start date + 1
Treatment Emergent AE (TEAE)	An AE will be considered as treatment-emergent if the time of onset is on or after the time of the first study drug administration or any AE that exist prior to first dose and if it increased in severity during the study
IOP	IOP will be measured at least twice in each eye with the right eye measured first. If the difference of the first 2 measurements is ≤ 1 mm Hg, the average of these 2 measurements will be used as the IOP data for this eye. If the difference is > 1 mm Hg, a third measurement will be taken, and the median of these 3 measurements will be used as the IOP data for this eye.

 Statistical Analysis Plan Sponsor: Sun Pharmaceutical In	ndustries Ltd		
		Date: 20 Sep 2023	

Variable / Term	Definition / Way of calculation
	In order to maintain the double-blind nature of the study, all study-related individuals, including the subjects, ancillary study site staff, clinical monitor(s), Investigator, Sponsor, and CRO staff, will remain blinded to the administered treatment.

8.4 Protocol Violation/Deviation

The relevant protocol violations/deviations have to be defined by a systematic data review prior to database closure. For this purpose, protocol violations that occurred during the study such as violations of inclusion/exclusion criteria or forbidden concomitant medications or patient non-compliance will be assessed as 'major' or 'minor' depending on their potential to interfere with the objectives of the study. Listings will be prepared to show the eligibility of all patients. Comprehensive justification for the classification of a protocol violation/deviation as "major" will be given in the integrated clinical study report.

A separate Protocol deviation listing will be prepared for the patients who discontinued the study or could not able to continue the study treatment or could not visit the study center or any procedure could not be performed.

8.5 Data Handling

8.5.1 Imputation of Missing data

Efficacy:

The analyses of the efficacy variable IOP) will be completed on observed data only (without imputation).

Safety:

To handle missing or partial AE and concomitant medication dates, the following rules will be applied.

For partial start dates:

The below table will illustrate how the imputation to be performed for unknown date/month/year.

DD	MM	YYYY	Imputation	
Known	Known	Unknown	Do not impute the date but assign a missing value.	
Known	Unknown	Known	a. If the year matches the year of the dose date, then impute the month and day of the dose date.b. Otherwise, assign "January."	
Unknown	Known	Known	a. If the month and year match the month and year of the first dose date, then impute the day of the dose date. b. Otherwise, assign "01."	

For partial end dates:

The below table will illustrate how the imputation to be performed for unknown date/month/year.

			Analysis Plan un Pharmaceutical Industries	Ltd
				Date: 20 Sep 2023
DD	MM	VVVV	Immutation	

DD	MM	YYYY	Imputation	
Known	Known	Unknown	Do not impute the date but assign a missing value.	
Known	Unknown	Known Assign month as "December."		
Unknown	Known	Known	Assign last day of the month	

After implementing the rules above, to determine whether AEs (or medications) with missing start or stop dates are pretreatment or on/after treatment, the following strategy will be used:

- 1. If the start date and stop date are both missing, then the most conservative approach is taken, and the AE (or medication) is considered to be treatment emergent (or concomitant medication).
- 2. If the start date is missing but the stop date is not missing and is on or after the day of study dose administration, then the most conservative approach is taken, and the AE (or medication) is considered to be treatment emergent (or concomitant medication).
- 3. If the start date is missing but the stop date is not missing and is before the day of study dose and after the date of signed informed consent, then the AE (or medication) is considered to be before treatment (or prior medication).
- 4. If the start date is not missing but the stop date is missing, then the most conservative approach is taken, and medication is considered to be concomitant while the AE is defined by start date.

If the Adverse Event Relationship flag is missing, the relationship for adverse event will be imputed and will be considered as related. If the Adverse Event Severity flag is missing, the severity will be imputed with the maximum severity will be considered as severity.

[figure not shown]

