#### 9.4 Eliciting, Documentation and Reporting of Adverse Events

Information on AEs will be derived by questioning the subjects in general terms (e.g., "How do you feel?" or "How have you been feeling since the last questioning?" respectively), by subjects' spontaneous reports, or by observation.

Adverse events will be documented on the source document. Trained monitors will check the entries on the source document. The AE will be transcribed to the AE eCRF-sections. The following information will be given for each AE: description of the AE, start date, stop date, severity, pattern, action taken, outcome, seriousness, dose of study drug, and relationship to the study medications. The dose of study medication assigned to an AE will be the dose the subject was assigned to take on the date the subject reported the AE first began.

The AE/SAE collection period for safety surveillance begins when the subject signs the ICF and continues until the end of treatment visit or until the last dose of study medication for subjects with early discontinuation. Adverse events with an onset before the subject receives first dose of the study medication will be categorized as non-treatment emergent AEs (non-TEAEs). Adverse events with an onset after at least 1 dose of study medication is received will be reported as TEAEs.

Safety reporting is inline with the local regulatory requirements in which the study will be conducted.

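### SAP 8.5.1 imputes a partial AE start as the first-dose date without checking the stop date, so an AE that ended before dosing can be counted as treatment-emergent

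*SAP*

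**What the plan says.** SAP 8.5.1 has a table for partial start dates, a table for partial end dates, and four numbered classification rules.

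- **Start, day unknown:** "If the month and year match the month and year of the first dose date, then impute the day of the dose date"; otherwise the day is set to 01.
- **Start, month unknown:** "If the year matches the year of the dose date, then impute the month and day of the dose date"; otherwise January.
- **Start, year unknown:** the date is not imputed and is left missing.
- **End, day unknown:** "Assign last day of the month".
- **Order:** the numbered rules are introduced with "After implementing the rules above, to determine whether AEs (or medications) with missing start or stop dates are pretreatment or on/after treatment".
- **Rule 3:** it opens "If the start date is missing but the stop date is not missing and is before the day of study dose". If the stop is also after consent, the AE is classed as before treatment.

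SAP 8.3, repeated in 9.6.3.1, then says "An AE will be considered as treatment-emergent if the time of onset is on or after the time of the first study drug administration". It adds AEs already present before dosing that worsen during the study. Protocol 9.4 says "Adverse events with an onset before the subject receives first dose of the study medication will be categorized as non-treatment emergent AEs (non-TEAEs", and has AEs collected from signature of the consent form.

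**The concern.** Neither start-date row refers to the stop date. A complete stop date before the first dose proves that onset was also before the first dose, yet both rows can move the start to the day of dosing. The event then enters the TEAE tables and appears in the listings as having started after it ended.

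The plan also becomes inconsistent with itself. If nothing is known about the start, rule 3 gives the right class. If the month is known, the imputation table gives the wrong one. More information produces a worse answer.

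Such events can occur in this trial. Screening lasts up to 42 days and includes washout (Protocol 6.1 and 6.3.1), and AEs are recorded throughout. At stake is the accuracy of the descriptive safety comparison, which serves the secondary objective. SAP 8.5.1 also sets a missing causality flag to related, so a misclassified event with that flag missing would reach the treatment-related TEAE table as well.

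**Working it through.** The plan states no figure for this point. The check is to apply the rules in their stated order.

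**Worked example (dates assumed).** First dose 20 June 2022; consent 42 days earlier, on 9 May 2022; AE stop date fully recorded as 10 June 2022. Imputed dates are compared with the first dose as calendar dates.

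| Recorded start | Start after the table | Deciding step | Class |
|---|---|---|---|
| Complete, 5 June 2022 | 5 June 2022 | Onset before dose | Pre-treatment |
| Day unknown, June 2022 | 20 June 2022 | Onset on dose date | Treatment-emergent |
| Day 5, month unknown, 2022 | 20 June 2022 | Onset on dose date | Treatment-emergent |
| Wholly missing | Missing | Rule 3: stop before dose and after consent | Pre-treatment |

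In rows two and three the start falls 20 − 10 = 10 days after the stop. Row three also overwrites a day that was known.

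**Does a later rule correct this?** Rules 1 to 3 all need a missing start. Rule 4 covers a start that is present with a missing stop. After imputation this record has both dates, so none of the four applies and the definition in SAP 8.3 decides. Nothing in the SAP says that an imputed start may not be later than the stop.

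**Scope.** Three conditions are needed:
1. The start is partial.
2. Its known part matches the month and year of the first dose (or the year, if the month is unknown).
3. The stop date is complete and before the first dose.

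If the stop day is also unknown in the dosing month, the stop goes to month end. The event is again treated as treatment-emergent, but without the reversed dates.

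**How often the rule bites, given a partial start (illustrative only).** Take every first-dose day in 2022 (365 days), every onset from 1 to L days before dosing, and every stop from onset to the day before dosing, all equally weighted. The number of combinations is 365 × L(L + 1)/2; for L = 7 that is 365 × 28 = 10,220. The share of these resolved pre-dose events that becomes treatment-emergent is:

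| Onset within L days before dosing | Combinations | Day unknown | Month unknown |
|---|---|---|---|
| 7 | 10,220 | 84% | 99% |
| 14 | 38,325 | 68% | 97% |
| 28 | 148,190 | 38% | 95% |
| 42 | 329,595 | 17% | 92% |

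Every reclassified event has its start after its stop, because the stop is always before dosing and the imputed start is the dosing date. These shares apply only to AEs that have a partial start and ended before dosing. They say nothing about how many such AEs exist.

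**The case against.** The strongest defence is that imputing towards the first dose is deliberately conservative and the consequence is slight. Protocol 9.4 asks for a start and stop date for every AE, AEs are assessed at the baseline visit, and Protocol 11.5 provides for discrepancy queries, so qualifying records should be few. TEAEs are summarised without hypothesis tests. SAP 8.1 has all data listed, so the recorded stop date stays visible. All of this stands as a limit on size. Conservatism does not justify the rule itself: it settles doubt about timing, and a complete stop date before dosing leaves none. Rule 3 declines the conservative option in exactly this situation.

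One could also read missing in rule 3 as including partial dates. The text does not favour this. The rules run after imputation, and the start-date table assigns a missing value only when the year is unknown. Even on that reading, the imputed start would still follow the stop.

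A reader might infer three stronger points that the documents do not support:

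- **Washed-out medication becoming concomitant.** SAP 9.4 classifies medication by end date, so a drug with a complete end date before dosing stays prior. A partial end date can move past the first dose, but SAP 9.4 openly treats an unknown end date as concomitant. Capping imputed end dates at last study contact would not reverse the switch, because last contact falls after the first dose for any dosed subject who is followed up.
- **Damage to the per-protocol set.** SAP 8.4 bases deviations on a data review with judgement about major or minor. Nothing says they are programmed from imputed dates, and discontinuation of IOP-lowering medication has its own record (Protocol 6.3.1, SAP 9.6.3.9).
- **Negative AE durations in the results.** SAP 8.3 defines duration of exposure only, and no AE duration summary is planned. The visible fault is a reversed pair of dates in a listing.

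**Conclusion.** The point holds for adverse events only. As written, SAP 8.5.1 gives the wrong class to an AE with a matching partial start and a complete stop date before the first dose, against Protocol 9.4 and against rule 3's result for a wholly missing start.

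It is a minor point. It affects descriptive TEAE counts and listings, not the primary endpoint or any test. The number of affected records cannot be derived from the documents and is probably small. Because the events precede dosing in a randomised comparison, little bias between arms is expected; counts would be somewhat inflated in both. The conclusion assumes that the rules are programmed literally and in the stated order. The percentages above rest on equal weighting of dates and are not estimates for this trial.

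**What to change.** Add to SAP 8.5.1, ahead of the start-date table: if an AE's stop date is complete and before the first dose, the AE is pre-treatment, unless it meets the worsening criterion in SAP 8.3, and its imputed start may not be later than its stop date; in all other cases the existing rule applies.

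Both the day-unknown and the month-unknown rows need this condition. It brings the table into line with rule 3 and Protocol 9.4. The cost is one sentence and one programming condition, with no new data. SAP section 11 has the SAP finalised before database lock, so the change belongs before that step.
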